2.12 SMS Interventions

All three SMS interventions work iteratively primarily through once-weekly dialogue sessions or micro-interventions and use behavior change techniques (BCTs) including self-monitoring with performance feedback and goal support. Each SMS intervention will differ in the content of queries and feedback, which is tailored to the target risk behavior. SMS queries and subject responses are stored and time-stamped in a database. Branching logic is used to tailor SMS feedback and queries. At the completion of 6-weeks, all SMS intervention participants will be asked to complete another 6 weeks of SMS assessments without receiving any feedback or goal support. This is to serve as a washout period so that durability can be assessed at week 14. All queries, feedback libraries and branching logic will be written prior to trial enrollment. *See Appendix for SMS Intervention Material*.

2.13 SMS vehicle safety self-monitoring (i.e. assessment control)

Participants allocated to the control arm will simply continue to receive weekly SMS assessments related to their target risk behavior without receiving any feedback or goal support for 12 more weeks.

2.14 Outcome Assessments & Blinding

The primary outcomes will be the percentage of participants in each treatment arm who report vehicle risks at week 8 (immediate effects) and week 14 (durable effects). Questions are the same as those used in screening. Participants will receive a text prompting them to log in to the secure web site to complete the 21-question survey which should take them no more than 10 minutes to complete. Research associates and investigators will be blinded to the allocation until outcome evaluation. It is not possible to blind subjects given the nature of the intervention. We do not expect any scenarios where emergency unblinding will be necessary.

2.15 Compensation

Participants will be compensated \$15 for completing enrollment procedures. We will add \$15 if they meet run-in criteria at the end of week 2 and complete the 8-week follow-up assessment. We will add a final \$15 if they complete the 14-week assessment.

2.16 Regulatory Issues

We will submit an IRB protocol both for the trial and coordinating center at the University of Pittsburgh. We will also submit an IRB protocol at the University of Pennsylvania. We expect the trial to be minimial risk to participants, given that the only possible risk will be from potential breach of confidentiality. We will minimize these risks through various strategies. The trial will be registerted on ClinicalTrials.gov.

2.17 Contingencies and Participant Withdrawal

- In the unlikely event that a participant is discharged from the ED prior to completing enrollment procedures, we will make every attempt to assist the participant in completing them in the following 48 hours. Those participants who still do not complete in this time period will be withdrawn from the study.
- If a participant withdraws from the study, further communication will be stopped. Data collected prior to withdrawal will be maintained but additional data will not be collected.

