2.6 Contact Information

Participants will be asked to provide us with their contact information (name, phone number, email). We will also ask them to provide a social security number, as it is required for participant payment.

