Day & Time Incoming Outgoing Enrollment Hi [_NAME_]. Welcome to to the SaVE Study For the next 2 weeks, each Sunday, we will ask you about your seat belt use in the past week If you complete at least 50% of the text queries, you will be eligible for the rest of the study Any If at any time you wish to stop receiving texts, just text us "stop" response Sunday, 4pm Hi [_NAME_], it's theSaVE Team checking in How often have you been a passenger or driver in a car the past week? 0=never; 1=a few times; 2=most days; 3=every day [Missing] We missed your response. Text us how often you have been a passenger or driver in a car the past 2 hours x1 week [Missing] 2 hours х2 You must be busy. We will check in next week [Nonsense We don't understand. Please text us a response option: 0=never; 1=a few times; 2=most days; 3=every 1 day 0 ΟK 1,2,3 How often did you wear a seat belt? 0=never; 1=a few times; 2=most of the time; 3=every time [Missing] 1 hour x1 We missed your response. Text us how often you wore a seatbelt [Missing] 1 hour You must be busy. We will check in next week x2 We don't understand. Please text us a response option: 0=never; 1=a few times; 2=most of the time; [Nonsense 3=every time 1 0,1,2,3 Thanks Day 15 Due to your low response rate, you will be withdrawn from the SaVE Study (Monday) For further information about seat belt safety, go to www.NHTSA.gov

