Appendix: SMS Interventions: Seat belt Safety

Day & Time	Incomin	Outroing
Day & Time Qualified Week 3,	g	Outgoing
Monday, 5pm		
Qualified		Congratulations [Name]! You have qualified to continue the SaVE Study For the next 6 weeks, we will help you set goals and provide you personalized feedback on your seat belt use We will check in next Sunday. Until then, take care
Week 3-8: Sunday, 3pm		
2 hours 2 hours	[Missing] x1 [Missing] x2 [Nonsen se]	Hi [_NAME_], it's the SaVE Study Team checking in How often have you been a passenger or driver in a car the past week? 0=never; 1=a few times; 2=most days; 3=every day We missed your response. Text us how often you have been a passenger or driver in a car the past week? You must be busy. We will check in next week We don't understand. Please text us a response option: 0=never; 1=a few times; 2=most days; 3=every day
1 hour	0 1,2,3 [Missing] x1	OK When in the car, how often did you wear a seat belt? 0=never; 1=a few times; 2=most of the time; 3=every time We missed your response. Text us how often you wore a seat belt
1 hour	[Missing] x2 [Nonsen se]	You must be busy. We will check in next week We don't understand. Please text us a response option: 0=never; 1=a few times; 2=most of the time; 3=every time
If Goal Not Set	3	[Posiitve Reinforcement Message]
	0,1,2	[Social Norms Message]
If Goal Set	Goal met Goal not met	[Goal Met Message] [Goal Not Met Message]
		Would you be willing to commit to a goal to wear a seat belt every time this week?
1 hour	[Missing] x1 [Missing]	We missed your response. Text us whether you'd be willing to set a goal?
1 hour	x2 [Nonsen se]	You must be busy. We will check in next week We don't understand. Please text us either yes or no
No Goal	No	[No Goal Roll Library Message]
Goal +	Yes	[Goal Reinforcement Message]
Random 2 days per week, 4pm		
lf goal -		[Seat belt Safety Info Message]
lf goal +		[Goal Reminder Message]

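### Someone who texts 'stop' after randomisation has no stated route to the week-8 and week-14 surveys, and the protocol does not say whether 'stop' counts as withdrawal

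*Combined protocol and SAP*

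**What the plan says.** The run-in scripts for all three cohorts (Appendix, SMS Run-In) carry the same opt-out at enrolment. It begins "If at any time you wish to stop receiving texts" and tells the participant to text the word 'stop'.

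The primary outcome is taken from a web survey at week 8 and repeated at week 14. Section 2.14 gives one prompt for it: "Participants will receive a text prompting them to log in to the secure web site". Section 2.6 shows that other contact details are held: "Participants will be asked to provide us with their contact information (name, phone number, email". No section gives the email address or a telephone call any part in follow-up.

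Section 2.17 sets the withdrawal rule: "If a participant withdraws from the study, further communication will be stopped". It continues: "Data collected prior to withdrawal will be maintained but additional data will not be collected". Section 6.2.2 says only that people may withdraw by contacting the team.

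Three further rules bear on the point:
- Section 4.2.3 fills a missing week-8 or week-14 outcome from the weekly SMS reports, then from the worst SMS report in weeks before or after the gap. Chained multiple imputation is a sensitivity analysis.
- Section 4.2.1 restricts every analysis to participants who answered at least one week of SMS assessments in the intervention period.
- Control participants receive weekly assessments only (2.13). The seat belt intervention adds feedback, a goal prompt and its reminders to the Sunday dialogue, and schedules further messages under the entry "Random 2 days per week, 4pm".

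**The concern.** Wanting fewer texts is different from wanting to leave a trial, but the protocol makes no distinction between the two. Because the outcome prompt uses the same channel as the intervention, ending the texts also ends the stated means of asking for the outcome.

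Opting out after randomisation is a response to the assigned programme by participants who know what they are receiving. If intervention participants who disliked the messages leave observation more often than controls, and still have the risk behaviour, the week-8 comparison may favour the intervention. The week-14 durability comparison is exposed in the same way. So is the acceptability item on helpfulness, which sits in the week-8 survey and would miss those who disliked the texts enough to end them.

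**Working it through.** **1. The two readings of 'stop'.**
- *It means withdrawal.* Section 2.17 then ends contact and bars further data, so no survey is obtained.
- *It ends texts only.* The participant is still in follow-up and 2.17 does not apply, but the text in 2.14 is no longer sent and no other prompt is described.

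Neither reading leaves a stated route to the survey.

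**2. What the imputation can recover.** Take a participant who stops in week 4. The week-8 survey looks back two weeks, to weeks 7 and 8. There are no SMS reports for those weeks or for weeks 6 and 9 beside them. Read as adjacent weeks, the rule in 4.2.3 gives no value. Read as any earlier week, it gives one at least three weeks old. For week 14 the gap is wider. A participant who stops before any intervention-period reply is removed by 4.2.1. A participant who stops late, with SMS weeks near week 8, is covered reasonably well.

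**3. The plan's own figures (section 4.1).** Inputs: 25% versus 10% always belted, two-sided alpha 0.05, power 80%, pooled variance.

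n = [1.960 × √(2 × 0.175 × 0.825) + 0.842 × √(0.25 × 0.75 + 0.10 × 0.90)]² / 0.15² ≈ 99.5, so 100 per arm, as stated.

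Attrition: 300 × 0.90 × 0.80 = 216, or 108 per arm, with 83.1% power. If week-8 completion in the intervention arm fell from 80% to 70% (94.5 versus 108 analysed), complete-case power would still be 80.8%. Power is not the main issue.

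**4. Contact load, weeks 3 to 8.** Intervention: 6 × (1 Sunday + 2 random days) = 18 days. Control: 6 × 1 = 6 days.

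**5. Illustrative bias in a stayers-only comparison.** The documents give no opt-out rates, so everything here except the 75% and 90% is assumed. Stayers have the plan's Cohort 1 risks, 75% and 90%, a difference of 15 points. Control opt-out is 5%, intervention opt-out is s, and the risk among stoppers is r.

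All-randomised risk: intervention (1 − s) × 0.75 + s × r; control 0.95 × 0.90 + 0.05 × r.

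With r = 0.95, control is 90.25%:

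| s | Intervention risk | True difference | Overstatement |
|---|---|---|---|
| 10% | 77.0% | 13.25 | 1.75 |
| 15% | 78.0% | 12.25 | 2.75 |
| 20% | 79.0% | 11.25 | 3.75 |

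The extremes are r = 0.90 with s = 10% (90.0 − 76.5 = 13.5, overstated by 1.5) and r = 1.00 with s = 20% (90.5 − 80.0 = 10.5, overstated by 4.5). With equal 5% opt-out and r = 0.95 the intervention risk is 76.0%, the difference 14.25 and the overstatement 0.75. That part is not due to imbalance.

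**6. The same case if every stopper is scored as at risk.** Control becomes 0.855 + 0.05 = 90.5%. Intervention becomes 77.5%, 78.75% and 80.0%. The differences are 13.0, 11.75 and 10.5, against true values of 13.25, 12.25 and 11.25. The error is now 0.25 to 0.75 points against the intervention.

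**The case against.** A reader might infer that 'stop' is withdrawal, so that 2.17 forbids outcome collection and the primary outcome is simply lost. The documents do not support that. The scripts say only that the texts end, 2.17 speaks of leaving the study, and 6.2.2 does not mention the keyword. Section 2.14 says that a text is sent but does not exclude other contact, and nothing forbids emailing someone who has not withdrawn. The consent pages were not available for this review and may address the matter. What stands is that the protocol leaves the question open and describes no other route.

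The missing-data rule also counts for the plan. Earlier SMS reports are kept, and where the rule scores a stopper as at risk, step 6 shows the favourable bias disappearing. Its weakness is confined to those who stop early.

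The run-in screens out non-responders, and a 'stop' during it precedes randomisation and cannot unbalance the arms. The unequal text load ends at week 8, and the plan already allows for 20% non-completion at that point. All of this is correct. The allowance, however, protects sample size and does not protect against unequal loss.

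**Conclusion.** The gap is real and cheap to close. A post-randomisation text opt-out has no stated route to the directly observed week-8 or week-14 outcome under either reading of 'stop', and the SMS reports that would support imputation end at the same moment.

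A reader might go further and conclude that the intervention arm will lose more participants and that the result is biased by a known amount. The documents do not show this. The 18 versus 6 contact days make unequal opt-out plausible, but no opt-out rate is given for either arm and section 4.1 uses one completion rate for both. The 1.5 to 4.5 points rest on 5% versus 10-20% opt-out, on 90-100% of stoppers being at risk, and on a stayers-only comparison that is not the planned analysis. Under the plan's imputation the figure would be smaller wherever stoppers are scored as at risk. This should be changed, as a protection against possible bias.

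**What to change.** - In 2.14 and 2.17, state that 'stop' ends texts only. Send those participants the week-8 and week-14 survey links at the email address already collected, unless they decline, with the survey payments in 2.15 unchanged.
- Apply the bar on additional data in 2.17 only to full withdrawal from the study.
- Amend 4.2.1 so that an emailed week-8 response enters the primary analysis even when the participant sent no SMS in the intervention period. Without this, the earliest stoppers would answer the survey and still be excluded.
- Report text opt-outs and full withdrawals separately, by arm.

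The cost is an IRB wording change and up to two emails to people who opted out of texts, which they can decline. No visits or participants are added. Stoppers who do not answer the email remain missing and still depend on the imputation rule.

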2.18 Study flow diagram

3. OUTCOMES

3.1 Definitions

3.1.1 Primary Outcome

-Percentage of participants who report a vehicle risk at week 8.

- d. Cohort 1: Any vehicle trip in past 2 weeks where individual reports not using a seat belt
- e. Cohort 2: Any vehicle trip in past 2 weeks where individual reports phone was used to type while driving and car was moving
- f. Cohort 3: Any vehicle trip in past 2 weeks where individual reports driving a vehicle within 3 hours after consuming 3 or more drinks

3.1.2 Secondary Outcomes: Feasibility

-Percentage of ED patients who screen positive and agree to enroll -Percentage of ED patients who enroll who meet run-in criteria.

3.1.3 Secondary Outcomes: Acceptability

-Percentage of ED patients enrolled in the Intervention arm who complete at least 50% of the SMS assessments during the intervention period.

-Percentage of ED patients enrolled in the Intervention arm who found the program helpful.

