2.10 SMS Run-in

All participants will complete a 2-week run-in period where they complete weekly SMS assessments related to their target risk behavior without receiving any feedback or goal support. The primary purpose of the run-in is to exclude noncompliant subjects. Only participants who respond to at least 50% of the SMS queries in week 1 & 2 will be eligible to continue in the study. The secondary purpose is to identify the post-enrollment/ pre-intervention vehicle risk behaviors that may occur as a result of assessment reactivity. We expect that simply the act of enrolling in a study about vehicle risk and completing weekly SMS assessments of risk may result in reduced risk behaviors.

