4. SAMPLE SIZE CALCULATION AND STATISTICAL ANALYSIS PLAN

4.1 Sample size calculation

The study has been powered to have at least 80% power for the primary outcome for Cohort 1 (seat belt use). Based on Sommers et al., 2013, we can likely expect the intervention to increase the percentage of subjects reporting seat belt use by15% on top of self-monioting alone. Using a 2-sample test of proportions, estimating 25% of the intervention participants and 10% of the control (SMS self-monitoring) report always seat beltuse, we would need around 100 subjects per group to show a significant difference between arms. Expecting 10% drop-out in the SMS 2-week run-in and 80% completing 8-week assessments, 300 enrolled in the ED should provide an analyzed sample of 216 (108 per arm).

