4.2 Statistical analysis plan

4.2.1 General considerations

The statistical analyses and reporting will adhere to the CONSORT guidelines. All tests will be twosided, a p-value < 0.05 will be considered significant, and all confidence intervals will have 95% coverage. All analyses will be conducted on a modified intention-to-treat basis only including participants responding to at least one week of SMS assessments during the intervention period. The two groups will be compared in relation to baseline characteristics using descriptive statistics. The persons conducting the statistical analysis will be blinded to the randomized allocation. Groups will be designated as "A" and "B" until all pre-specified analyses are performed and shared with all authors.

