Questi on	How dangerous is it to type on your phone while driving?	Not at all	Somew hat	Very	Comple tely			
Code	danger_twd	0	1	2	3			
Questi on	How much do you agree: I have complete control over whether I type on my phone while driving.	Strongly Disagree	Disagre e	Somew hat Agree	Mostly agree	Stron gly Agree		
Code	control_twd	0	1	2	3	4		
Questi on	Check off all the reasons you have driven a car after drinking alcohol?	l had no other opiton	l don't think it affects my driving	lt's not a big deal	l am careful	lt is fun	l do not drive after dirnki ng alcoh ol	l do not dri ve
Code	dd reasons	0	1	2	3	4	5	6
Questi on	How often do your friends drive after drinking alcohol?	Never	Rarely	Most of the time	Always			
Code	friends_dd	0	1	2	3			
Questi on	How dangerous is it to drive soon after drinking more 3 or more alcoholic drinks?	Not at all	Somew hat	Very	Comple tely			
Code	danger_dd	0	1	2	3			
Questi on	How much do you agree: I have complete control over whether I type on my phone while driving.	Strongly Disagree	Disagre e	Somew hat Agree	Mostly agree	Stron gly Agree		
Code	control_dd	0	1	2	3	4		

Questi on	Did you find the text message program helpful?	Not at all	Somew hat	Very much
Code	helpful	0	1	2
Questi on	Would you recommend the program to others?	No	Yes	
Code	recom	0	1	
Questi on	Any other comments you'd like to provide that could help us make the text message program better?			
Code	comments			

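### Both acceptability percentages describe run-in passers in one arm; the mITT rule inflates completion, and missing 'helpful' answers have no rule

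*Combined protocol and SAP*

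**What the plan says.** - **Run-in.** Section 2.10: "Only participants who respond to at least 50% of the SMS queries in week 1 & 2 will be eligible to continue". Arms are assigned only afterwards (2.11). The typing-while-driving intervention appendix shows what the threshold means in practice: one of the two Sunday assessments.
- **Acceptability, 3.1.3.** The first outcome is "Percentage of ED patients enrolled in the Intervention arm who complete at least 50% of the SMS assessments during the intervention period". The second is the percentage of the same arm who found the programme helpful. Section 4.2.3 reports each with a 95% confidence interval, and neither is given for the control arm.
- **Analysis set, 4.2.1.** All analyses are restricted to participants who answered at least one weekly assessment in the intervention period.
- **Control arm, 2.13.** Controls "will simply continue to receive weekly SMS assessments related to their target risk behavior", without feedback or goal support, for 12 more weeks.
- **Source of 'helpful'.** The item is "Did you find the text message program helpful", with three answers (not at all, somewhat, very much). It is in the 8-week survey and absent from the 14-week survey.
- **Missing data.** Section 4.1 plans on "Expecting 10% drop-out in the SMS 2-week run-in and 80% completing 8-week assessments". The imputation rule in 4.2.3 covers vehicle risk behaviour and nothing else.
- **Related outcome.** The percentage of enrolled patients who pass the run-in is a feasibility outcome in 3.1.2.

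**The concern.** The synopsis lists both figures among the key secondary outcomes. Three features make them hard to interpret.

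First, what separates the arms is feedback and goal support, but the completion outcome counts the weekly assessments, which both arms receive. A high figure in the intervention arm could equal that of plain monitoring or fall below it. The control data that would tell these apart are collected, but section 4.2.3 names no comparison of completion by arm.

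Second, a participant who answers no intervention-period week cannot reach 50% and is a certain failure on this outcome. The restriction in 4.2.1 takes exactly these people out of the denominator, while 3.1.3 words the denominator as the patients enrolled in the arm. The two sections are not reconciled.

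Third, 'helpful' has no cut-point on its three levels and no rule for non-response. Missing answers could be informative: participants may text to stop at any time, and after withdrawal no further data are collected (2.17). A percentage among responders could then be read as the view of the whole arm.

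**Working it through.** **Inputs.** From 4.1: 300 enrolled in Cohort 1, 10% lost in run-in, 80% completing week 8. From 2.11: 1:1 randomisation after run-in. The documents give no expected value for either acceptability outcome, so the observed rates of about 80% below are assumptions.

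**1. The plan's own figures.** With "estimating 25% of the intervention participants and 10% of the control (SMS self-monitoring) report always seat beltuse" and a two-sided 5% level, the pooled two-proportion formula without continuity correction gives
n = [1.96·√(2·0.175·0.825) + 0.8416·√(0.25·0.75 + 0.10·0.90)]² / 0.15² = 99.5, so 100 per arm. This matches the plan. Retention: 300 × 0.90 × 0.80 = 216, or 108 per arm, which also matches. Nothing below changes these numbers.

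**2. Denominators for the intervention arm.** Randomised: 300 × 0.90 / 2 = 135. With a week-8 answer: 135 × 0.80 = 108. Missing: 135 − 108 = 27.

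**3. 'Helpful'.** Assume 86 of the 108 responders say helpful.
- Responders only: 86/108 = 79.6% (Wilson 95% interval 71.1% to 86.1%).
- All randomised, missing counted as not helpful: 86/135 = 63.7% (55.3% to 71.3%).
- All randomised, missing counted as helpful: (86 + 27)/135 = 113/135 = 83.7%.

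The range is 27/135 = 20 points wide, whatever rate is assumed among responders. The responders-only interval stops at 71.1% and so does not reach the lower bound of 63.7%: it carries sampling error but not the missing answers.

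**4. Completion and the mITT rule.** Let c be the number completing at least 50%, and z the number answering no intervention-period week. Over all randomised the figure is c/135; under 4.2.1 it is c/(135 − z), which is larger whenever z > 0. With c = 108 (80%, assumed), the other 27 are all failures, so z lies between 0 and 27. The reported figure then lies between 108/135 = 80% and, at the logical extreme, 108/108 = 100%.

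For a more realistic size, suppose each person's weekly response probability follows a beta distribution whose mean is set so that 10% answer neither run-in week. The figures are percentages answering at least 3 of 6 weeks:

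| Beta a + b (smaller = more varied) | All enrolled | Run-in passers | Passers under mITT |
|---|---|---|---|
| 0.5 | 88.2 | 96.2 | 97.0 |
| 1 | 87.6 | 94.2 | 95.1 |
| 2 | 87.5 | 92.3 | 93.1 |
| 4 | 88.1 | 91.1 | 91.7 |
| 10 | 89.4 | 90.8 | 91.1 |
| 1000 | 91.6 | 91.6 | 91.7 |

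Run-in selection adds 0 to 8 points and the mITT rule adds up to about 1 more. The model has no permanent drop-out during the intervention; texting to stop would raise z and the second effect.

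**5. Completion over all enrolled.** If 80% of those randomised reach the mark (assumed), the share of enrolled patients lies between 0.90 × 0.80 = 72% and 72% + 10% = 82%, depending on what run-in failures would have done.

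**6. What an arm comparison would deliver.** With completion near 80% in both arms and 135 per arm, the 95% interval for the difference is ±1.96·√(2·0.8·0.2/135) = ±9.5 points. Cohorts 2 and 3 enrol 100 each; at the same run-in loss (assumed) they have 100 × 0.90 / 2 = 45 per arm, and the interval is ±1.96·√(2·0.8·0.2/45) = ±16.5 points.

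**The case against.** A reader might infer that the completion figure merely restates the entry filter. The documents do not support that. Passing the run-in takes one of two Sundays under plain monitoring, and only 10% are expected to fail. The outcome asks for half of six later weeks, with added feedback and goal texts. The modelled inflation from this selection is 0 to 8 points.

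The selection is also visible: the run-in pass rate is reported with an interval, so anyone can multiply the two figures. Arms exist only after run-in, so a percentage of the intervention arm is a coherent target. Counting run-in failures as people who rejected feedback they were never offered would go too far.

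Nor do the documents contain a responders-only rule for 'helpful'. Read literally, 3.1.3 takes the whole arm as denominator, and the gap is silence about missing answers. That dissatisfied participants answer less often is plausible but not shown; the bounds in step 3 lie on both sides of 80%.

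Finally, a one-arm descriptive percentage is an accepted measure of acceptability. No threshold or decision hangs on it, and section 2.1 calls outcomes beyond the powered seat belt comparison exploratory.

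All of this stands, and it limits the point. It does not answer the mITT exclusion of certain failures, the missing cut-point and non-response rule for 'helpful', or the lack of a control figure for assessments that controls also receive.

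**Conclusion.** The point holds as a modest one. Both figures describe run-in passers in one arm. Completion alone cannot separate engagement with feedback and goal support from engagement with weekly monitoring. If 4.2.1 is applied as written, completion is overstated whenever anyone in the arm answers no intervention-period week: by up to about 1 point in the model, and by more if participants leave by text. For 'helpful', the plan's own 80% retention leaves a 20-point range, 64% to 84% of those randomised for an assumed 86 of 108.

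A reader might go further and conclude that neither figure shows acceptability, or that the objective goes unanswered. That does not follow: each figure is informative about run-in passers once its denominator and missing-data rule are fixed. The sizes rest on Cohort 1 planning retention and on assumed response rates near 80%. The primary analysis and sample size are not affected.

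**What to change.** In sections 3.1.3 and 4.2.3:

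1. Report the at-least-50% completion percentage in both arms, and the intervention-minus-control difference with a 95% confidence interval. Take all randomised participants as the denominator and state that this outcome is exempt from the mITT restriction in 4.2.1.
2. Report 'helpful' over all randomised to the intervention arm. State which of the three answers count as helpful. Count non-responders first as not helpful and then as helpful, and show both results.
3. Optionally, show completion beside the run-in pass rate already reported under 3.1.2, so that the share of enrolled patients can be read off.

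The cost is a few table rows from data already collected, and headline acceptability figures that will probably look less favourable.
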